#### 7.5.1 Primary Efficacy Analysis

The primary estimand, comprising four components, is defined as follows:

- a) The target population consists of patients with acne vulgaris that are eligible to be included in the clinical trial based on the inclusion/exclusion criteria in the protocol. The ITT Analysis Set will include all randomized subjects. For the analysis, treatment will be assigned based upon the treatment arm to which subjects were randomized regardless of which treatment they receive.
- b) The primary variable is the change from baseline in facial inflammatory lesion count of an individual subject at Week 12.
- c) To handle intercurrent events such as use of rescue medications, the hypothetical strategy for estimand will be used. Data collected following receipt of rescue medication (if any) will be considered missing in the analysis.
- d) The population-level summary measures will be the population mean differences in the primary variable between each dose of imidolimab and placebo at Week 12.

A MMRM model will be used with treatment, visit (Weeks 2, 4, 8, and 12), treatment by visit interaction, and facial IGA score at baseline (Grade 3 vs. 4) as categorical covariates and the baseline value of response as the only continuous covariate; only the visits up to and including week 12 are used. An unstructured correlation (UN) matrix will be used to model correlation within a subject; if convergence is an issue, a Toeplitz structure may be considered. Subjects with missing data at Week 12 due to early discontinuation will be included in the model.

The least squares (LS) mean and the standard error of this mean with the corresponding two-sided 90% CI will be provided for each treatment based on the model. The LS mean difference between treatments (imsidolimab – placebo), as well as the corresponding two-sided 90% CI will be provided based on the model. Summary statistics and the results of statistical testing in facial inflammatory lesion count at Week 12 will be tabulated. The LS mean change from baseline as well as differences between treatments in facial inflammatory lesion count will be plotted across post-baseline visits by treatment in separate plots.

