### 3.3 Hypothesis Testing

The primary analysis for this study is to compare the mean facial inflammatory lesion count for imsidolimab at each dose with placebo during the treatment period, at a two-sided alpha = 0.10 level. Any

testing being performed for secondary or exploratory endpoints will be considered exploratory in nature based on a 2-sided alpha = 0.10.

$$H_0: \mu_{imsidolimab} - \mu_{Placebo} = 0 \text{ vs. } H_A: \mu_{imsidolimab} - \mu_{Placebo} \neq 0$$

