### 3.5 Sample Size

Approximately 120 subjects will be stratified based on facial IGA score at baseline (3 [moderate] vs. 4 [severe]) and randomized in a 1:1:1 ratio to receive one of the following study treatments:

- Imsidolimab 400 mg on Day 1, 200 mg on Days 29 and 57

- Imsidolimab 200 mg on Day 1, 100 mg on Days 29 and 57
- Placebo on Days 1, 29, and 57

Assuming a total of 10% of subjects will discontinue prior to Week 12, there will be approximately 108 evaluable subjects (36 subjects in each arm) at the end of Week 12.

The study has 80% power to detect a between-group treatment difference of 6.1 lesions in the primary endpoint of mean change from baseline in the facial inflammatory lesion count at Week 12, using a 2-sided, equal-variance two-sample t-test at the  $\alpha = 0.10$  level, with the assumption of a common standard deviation (SD) of 10.4 lesions. The assumption was based on Arazlo (tazarotene) acne Phase 3 Study Trial-301 results. **Table 1** shows more information on power from a set of scenarios of variability and between-group mean differences.

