### **7.5.4 Sensitivity Analyses**

A number of sensitivity analyses are planned to evaluate the robustness of the primary and secondary efficacy results.

For the primary efficacy endpoint, the following sensitivity analyses will be performed:

- Analysis of primary efficacy endpoint using the PP Analysis Set.
- Analysis of primary efficacy endpoint for adolescent subjects (age <16 years).
- Analysis of primary efficacy endpoint by age group ([12, 25) years,  $\geq 25$  years).
- Analysis of primary efficacy endpoint by age and sex (male and [12, 25) years, male and  $\geq 25$  years, female and [12, 25) years, female and  $\geq 25$  years)
- Sex (male, female) will be added to the MMRM as a categorical variable if this model can converge.

- Site will be added to the MMRM as a fixed categorical effect if this model can converge. Small sites (enrollment less than 5 subjects) will be pooled together.
- Smoking history (current smoker vs non-current smoker) will be added to the MMRM as a fixed categorical effect if this model can converge.
- The papule and pustule count will be summed and analyzed using a similar MMRM model as specified for the primary analysis for ITT Analysis Set.
- Multiple imputation with FCS method ([Section 7.1](#)).
- Tipping point analysis ([Section 7.1](#)).
- Prior to database lock and unblinding, the assumption of normality in the change from baseline in facial inflammatory lesion count will be checked by visually inspecting the distribution of the residuals. If the normality assumption is not met, a repeated measures model using a GEE approach with an alternative distribution or any transformation will be considered. An unstructured correlation matrix will be used in the model if GEE is decided to be used; a Toeplitz structure may be considered if convergence is an issue. However, the results from the primary efficacy analysis will be considered the primary efficacy results.

For the secondary efficacy endpoints listed in [Section 7.5](#), the following sensitivity analyses will be performed:

- Analyses of secondary efficacy endpoints using the PP Analysis Set.
- Multiple imputation with FCS method ([Section 7.1](#)).

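### The Toeplitz fallback for the primary MMRM does not require visit-specific variances; if used in its plain form it gives the wrong Week 12 standard error whenever variance differs between visits.

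*SAP*

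**What the plan says.** SAP 7.5.1 models change from baseline in facial inflammatory lesion count at Weeks 2, 4, 8 and 12 with an unstructured within-subject matrix. It then provides that "if convergence is an issue, a Toeplitz structure may be considered". SAP 7.5.2.7 repeats this for facial IGA. The other secondary lesion-count models, the DLQI/CDLQI models (SAP 7.5.2.1 to 7.5.2.6 and 7.5.2.11) and the continuous exploratory endpoints (SAP 7.5.3) refer back to the primary model, so they inherit the clause.

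The SAP does not name the Toeplitz variant, rank the fallbacks, or ask for robust standard errors if one is used. The only MMRM template in SAP Appendix 2 is unstructured with Kenward-Roger degrees of freedom, which implies model-based standard errors. Protocol 9.4.5 specifies an unstructured covariance and no fallback, and SAP Section 8 does not list the fallback as a change.

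The comparison of each dose with placebo is tested "at a two-sided alpha = 0.10 level", without multiplicity adjustment (SAP 7.5).

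**The concern.** A Toeplitz matrix is constant along its diagonals. Used directly as a covariance matrix, it gives every visit the same variance. The Week 12 standard error is then built from a variance pooled over Weeks 2 to 12. If residual variance rises towards Week 12, that standard error is too small: the test rejects too often and the 90% interval is too narrow. If variance falls, the reverse happens. Kenward-Roger corrects for small samples when the covariance form is right; it does not repair a wrong form.

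At stake are the level of the primary test and the coverage of its interval in the branch where the fallback is taken, and likewise in every model that borrows the clause. SAP 7.5.4 plans primary-endpoint analyses in subjects under 16, by age group, and in four age-by-sex cells. Ten covariance parameters are harder to estimate there than in the full sample. The same section makes three covariate-extended models conditional on convergence, so the SAP itself treats non-convergence as a live possibility.

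**Working it through.** **Inputs from the documents.** Two-sided alpha 0.10 (SAP 3.3). About 120 subjects randomized 1:1:1, so 40 per arm; 10% discontinuing before Week 12 leaves 120 × 0.90 = 108, or 36 per arm; SD 10.4 and difference 6.1 (SAP 3.5). Four post-baseline visits in the model (SAP 7.5.1).

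**Reproducing the plan's figure.** SAP 3.5 states: "The study has 80% power to detect a between-group treatment difference of 6.1 lesions". With 36 per arm, SE = 10.4 × √(2/36) = 2.451. Then 6.1/2.451 − 1.645 = 0.844 and Φ(0.844) = 0.80. The exact noncentral t gives 79.4%. The stated power is reproduced, and the point below does not affect it.

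**Parameter counts for four visits.** Unstructured: 4 × 5/2 = 10. Homogeneous Toeplitz: 1 variance + 3 lags = 4. Heterogeneous Toeplitz (TYPE=TOEPH): 4 variances + 3 lags = 7.

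**Assumption.** The documents give only one SD for this endpoint, 10.4. SDs at Weeks 2, 4 and 8 are therefore assumed, with Week 12 fixed at 10.4, over a range that includes flat and falling variance.

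**Large-sample formula.** The homogeneous fit settles close to the root-mean-square of the visit SDs, so

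- SE ratio r = √(mean of squared visit SDs) / 10.4
- actual error = 2 × [1 − Φ(1.645 × r)]

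Example, moderate growth: (7.5² + 8.5² + 9.5² + 10.4²)/4 = 326.91/4 = 81.73; the root is 9.04; r = 9.04/10.4 = 0.869; 1.645 × 0.869 = 1.430; error = 0.153.

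**Simulation under no treatment effect.** The primary model was fitted by REML with 40 per arm, 10% monotone dropout completely at random, baseline count and IGA as covariates, and correlation 0.7 per visit step. There were 1500 trials per scenario (Monte Carlo error about 0.008 near 0.10).

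| Assumed SD, Weeks 2/4/8/12 | Pooled SD | r | Error, formula | Error, simulated (homogeneous Toeplitz) | Mean model SE vs actual SD of estimate |
|---|---|---|---|---|---|
| 10.4 throughout | 10.40 | 1.000 | 0.100 | 0.097 | 2.42 vs 2.43 |
| 9/9.5/10/10.4 (mild growth) | 9.74 | 0.936 | 0.123 | 0.127 | 2.26 vs 2.43 |
| 7.5/8.5/9.5/10.4 (moderate growth) | 9.04 | 0.869 | 0.153 | 0.159 | 2.10 vs 2.43 |
| 5/7/9/10.4 (steep growth) | 8.11 | 0.780 | 0.200 | 0.194 | 1.87 vs 2.42 |
| 12/11.5/11/10.4 (falling) | 11.24 | 1.081 | 0.075 | 0.070 | 2.63 vs 2.44 |

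In the same simulated trials, the unstructured and heterogeneous Toeplitz fits gave errors of 0.094 to 0.099 in every row.

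**Dependence on correlation.** A second set of assumed SDs (8.5/9.2/10/10.4, 7/8.2/9.4/10.4, 5/7/9/10.4) was fitted under six correlation patterns (exchangeable, autoregressive and time-decaying). The errors were 0.131, 0.162 and 0.199 under all six. The variance profile drives the result; the correlation hardly matters.

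**Limits.** The simulation used fixed approximate degrees of freedom (103 unstructured, 200 homogeneous, 110 heterogeneous) in place of Kenward-Roger, normal data and an assumed correlation.

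**The case against.** Several stronger readings are tempting, and the documents do not support them.

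- A reader might infer that the SAP imposes equal variances. It does not: it leaves the variant unnamed, gives no Toeplitz code, and introduces the matrix as a model for correlation. A heterogeneous Toeplitz would satisfy the text. The documented gap is under-specification.
- A reader might infer that the test is bound to be liberal. Neither document says that variance grows. The model adjusts for baseline count, and the count model in SAP Appendix 2 is negative binomial, in which variance falls with the mean. If counts drop over 12 weeks, residual variance could drop too, and the test would be conservative. The sign is unknown.
- A reader might infer that the primary result is at risk. Three things must coincide: the unstructured fit fails, the team takes up an optional fallback, and it uses the homogeneous form while variances differ. Ten parameters from about 120 subjects at four visits should normally be estimable. That is a judgement, but a sound one.
- A reader might extend the point to SAP 7.5.4, where "a Toeplitz structure may be considered if convergence is an issue". That is a working correlation for a GEE, where inference ordinarily rests on empirical standard errors, and the Appendix 2 GEE templates request nothing else. The mechanism does not carry over.
- The unequal gaps between visits (2, 4 and 4 weeks) are no argument for this change, because heterogeneous Toeplitz also uses one correlation per lag.

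It is also fair that this is a Phase 2 trial informing internal decisions, and that heterogeneous Toeplitz relieves a convergence failure less than the plain form (7 parameters against 4). All of this limits the size and likelihood of the problem. It does not justify leaving the variant open, since the plain reading is the one that can distort the Week 12 inference.

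**Conclusion.** The point holds as a gap in pre-specification. If the unstructured fit fails and homogeneous Toeplitz is used with model-based standard errors, the nominal 0.10 error becomes about 0.12-0.13, 0.15-0.16 or 0.19-0.20 under mild, moderate or steep growth in SD. It is about 0.07 if SD falls and 0.10 if it is flat. Coverage of the 90% interval moves correspondingly, from about 80% with steep growth to about 93% with falling variance. These figures rest on assumed SDs at Weeks 2, 4 and 8; only the 10.4 comes from the plan. The branch is unlikely for the main primary fit and more plausible for the small age and age-by-sex fits. The sample size and power statement are unaffected. This is an inexpensive improvement to make before unblinding, and no reason to doubt the planned primary analysis when it runs as intended.

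**What to change.** In SAP 7.5.1 and 7.5.2.7, and through them in every model that refers to the primary MMRM, fix the order before the Week 12 unblinding:

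1. Unstructured.
2. If that does not converge, heterogeneous Toeplitz (TYPE=TOEPH), which keeps a separate variance for each visit.
3. Any homogeneous structure only as a last resort, with empirical (sandwich) standard errors and a named degrees-of-freedom method other than Kenward-Roger.

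Replace the permissive wording with this rule, add the fallback code to SAP Appendix 2, and list the fallback in SAP Section 8 as an addition to Protocol 9.4.5.

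The cost is a few lines of text and 7 − 4 = 3 more variance parameters than homogeneous Toeplitz, so slightly less relief when convergence fails. No new data and no change in sample size are needed.

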### **7.5.2 Secondary Efficacy Analyses**

#### **7.5.2.1 Percent Change from Baseline in Facial Inflammatory Lesion Counts at Each Visit**

Percent change from baseline in facial inflammatory lesion counts will be presented together with the primary endpoint. This endpoint will be analyzed using a similar MMRM model as specified for the primary endpoint. The percent change from baseline in facial inflammatory lesion counts will be the response variable in the model.

#### **7.5.2.2 Change from Baseline in Facial Inflammatory Lesion Counts at Visits Other Than Week 12**

This secondary endpoint will be presented together with the primary endpoint. Summary statistics and the results of statistical testing in facial inflammatory lesion counts at visits other than Week 12 will be tabulated. The change from baseline in facial inflammatory lesion counts will be analyzed using the same MMRM model as for the primary endpoint.

#### **7.5.2.3 Percent Change from Baseline in Facial Noninflammatory Lesion Counts at Each Visit**

Percent change from baseline in facial noninflammatory lesion counts at each visit will be analyzed using a similar MMRM model as specified for the primary endpoint. The percent change from baseline in facial noninflammatory lesion counts will be the response variable in the model.

#### **7.5.2.4 Change from Baseline in Facial Noninflammatory Lesion Counts at Each Visit**

Change from baseline in facial noninflammatory lesion counts at each visit will be analyzed using a similar MMRM model as specified for the primary endpoint. The change from baseline in facial noninflammatory lesion counts will be the response variable in the model.

#### **7.5.2.5 Percent Change from Baseline in Total Facial Lesion (Inflammatory and Noninflammatory Lesions) Counts at Each Visit**

Percent change from baseline in total facial lesion (inflammatory and noninflammatory lesions) counts at each visit will be analyzed using the MMRM approach defined for the primary endpoint. The percent change from baseline in total facial lesion (inflammatory and noninflammatory lesions) counts will be the response variable in the model.

#### **7.5.2.6 Change from Baseline in Total Facial Lesion (Inflammatory and Noninflammatory Lesions) Counts at Each Visit**

Change from baseline in total facial lesion (inflammatory and noninflammatory lesions) counts at each visit will be analyzed using a similar MMRM model as specified for the primary endpoint. The change

from baseline in total facial lesion (inflammatory and noninflammatory lesions) counts will be the response variable in the model.

#### **7.5.2.7 Change from Baseline in Facial IGA at Each Visit**

Change from baseline in facial IGA at each visit will be analyzed using a similar MMRM model as specified for the primary endpoint. The MMRM model will include treatment, visit, and treatment by visit interaction as categorical covariates and baseline facial IGA score as the only continuous variable. An unstructured correlation (UN) matrix will be used to model correlation within a subject; if convergence is an issue, a Toeplitz structure may be considered.

In addition, the following exploratory analyses will be performed:

- Change from baseline in facial IGA will be summarized in shift tables. In the shift table, for each treatment, the counts and percentages will be shown for baseline values crossed with each post-baseline timepoint. Agreement between the baseline score and each post-baseline score will be estimated with a weighted Kappa coefficient and corresponding 90% CI. A test of treatment difference for agreement will consist of a CMH test (ANOVA of row means) applied to a  $2 \times 3 \times 5$  Table (Baseline IGA facial strata  $\times$  treatment  $\times$  agreement score), where the agreement score is the Cicchetti-Allison weight used for the weighted Kappa coefficient, which is  $1 - |\text{difference}|/4$  for a 5 point score such as the facial IGA, so the value is =1 if there is perfect agreement,  $\frac{3}{4}$  if the scores are one category apart (in either direction),  $\frac{1}{2}$  if 2 apart,  $\frac{1}{4}$  if 3 apart and 0 if 4 apart. The latter score can happen only if baseline score is 4 and post-baseline score is 0.
- Change from baseline in facial IGA at Week 12 will be analyzed using an ordinal logistic regression model with treatment, facial IGA score at baseline (Grade 3 vs. 4) as categorical covariates. Odds ratios resulting from this model along with 90% CI will be reported.

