- ^f Refer to [Section 8.2.5](#) for details and instructions regarding the ECG. In addition to the time points specified in the SoA, ECGs may be performed at any time during the study if, in the opinion of the Investigator, it is clinically warranted.
- ^g If a negative QuantiFERON®-TB Gold test result was obtained within 6 months of screening, it can be skipped at screening. A chest X-ray will be administered per local standards, as required. The FSH testing is performed for women not of childbearing potential (postmenopausal women with at least 12 months of amenorrhea without an alternative medical cause). An adolescent subject who experiences menarche during the trial will be considered a WOCBP (refer to [Appendix 1](#) for definition of WOCBP) and will be required to follow the contraceptive guidance in [Appendix 1](#) and undergo scheduled pregnancy testing. Additional pregnancy testing may be performed whenever a menstrual cycle is missed or when pregnancy is otherwise suspected. Refer to [Appendix 10](#) for instructions regarding clinical laboratory parameters.
- ^h Refer to [Section 8.1](#) for details and instructions regarding facial lesion count, facial IGA, truncal (chest, neck, and back) IGA, PGI-S, PGI-C, DLQI (subjects \geq 16 years of age)/CDLQI (subjects $<$ 16 years of age), SSQ, and SSRS. Facial IGA must be performed before facial lesion count.
- ⁱ On Day 1, samples for PK will be collected at predose and 2 hr (\pm 10 min) post SC administration. See [Table 5](#).
- ^j Tape stripping will be performed for all randomized subjects as part of this study (not optional). Tape strips will be collected from non-lesional and lesional skin at Day 1 and Week 12 and from lesional skin at Week 4.
- ^k During the treatment period, subjects will receive either imsidolimab or placebo SC administered as follows: 400 mg imsidolimab, 200 mg imsidolimab, or placebo on Day 1; followed by 200 mg imsidolimab, 100 mg imsidolimab, or placebo on Days 29 and 57.
- ^l At screening, prior medications should be reviewed and documented. Refer to [Section 6.5](#).

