5.1 INCLUSION CRITERIA

To be eligible to participate in this study, a subject must meet all of the following criteria, either at the screening and Day 1 visits or only at one of the specified visits (screening or Day 1) as noted in the criterion:

1. Male and female aged 12 to 45 years (inclusive) at the time of signing the informed consent/assent.
2. Moderate to severe facial AV at Screening and Day 1, defined as follows:
 - a. Facial IGA score of 3 (moderate) or 4 (severe)
 - b. At least 20 and no more than 100 inflammatory lesions on the face
 - c. No more than 100 noninflammatory lesions on the face.
 - d. No more than 5 nodules (≥ 5 mm) on the face
3. Subject agrees to use Cetaphil Skin Cleanser on a regular basis (ideally once or twice daily) for at least 1 week prior to Day 1 and agrees to continue using Cetaphil Skin Cleanser at the same frequency throughout the study.
4. Subject must meet the following laboratory criteria at screening:
 - a. Hemoglobin ≥ 90 g/L (≥ 9 g/dL)
 - b. White blood cell count $\geq 3.0 \times 10^9$ /L ($\geq 3.0 \times 10^3$ / μ L)
 - c. Platelets $\geq 100 \times 10^9$ /L ($\geq 100 \times 10^3$ / μ L)
 - d. Serum creatinine < 132.6 μ mol/L (< 1.5 mg/dL)
 - e. Alanine aminotransferase (ALT) and aspartate aminotransferase (AST) ≤ 2 upper limit of normal (ULN)
 - f. Total bilirubin $\leq 1.5 \times$ ULN. Subjects with known Gilbert's disease who have serum bilirubin $< 3 \times$ ULN may be included
5. Body weight ≥ 40 kg and BMI within the range of 18 to 40 kg/m^2 for adults and 16 to 40 kg/m^2 for adolescents, inclusive { $\text{BMI} = \text{weight (kg)}/[\text{height (m)}]^2$ }.
6. Contraceptive use by men and women should be consistent with local regulations regarding the methods of contraception for those participating in clinical studies.
Contraception and pregnancy:
 - a. A male subject must agree to use contraception as detailed in [Appendix 1](#) of this protocol during the treatment period and for at least 200 days (which includes the duration of relevant exposure plus the duration of sperm cycle) after the last study treatment administration and refrain from donating sperm during this period.

- b. Female subjects:

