#### **7.5.2.8 Proportion of Subjects Achieving a Facial IGA of Clear (0) or Almost Clear (1) With at Least a 2-Grade Decrease from Baseline at Each Visit**

The frequency and percentage of subjects achieving a facial IGA of clear (0) or almost clear (1) with at least a 2-grade decrease from baseline will be summarized at each visit. The difference in percentage between each dose of imidolimab and placebo will be estimated by an unadjusted risk difference in proportions with 90% exact unconditional CIs. This will be performed overall and within each facial IGA stratum (Grade 3 or 4). The common risk difference will also be tested using a generalized CMH test (ANOVA for row means), adjusting for facial IGA at baseline (Grade 3 vs. 4).

An additional exploratory analysis will be performed by visit for the proportion of subjects achieving a facial IGA of clear (0) or almost clear (1) with at least a 2-grade decrease from baseline. A repeated measures generalized estimating equations (GEE) model with a logit link will be used. The model will include treatment, visit, treatment by visit interaction, and baseline facial IGA score as categorical covariates. Data from protocol-specified visits up to Week 20 will be included in the analysis. An unstructured correlation matrix will be used to model correlation within a subject; if convergence is an issue, a Toeplitz structure may be considered. An odds ratio resulting from this model along with 90% CI will be reported.

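### The facial IGA MMRM adjusts only for baseline IGA, which eligibility limits to two grades, and omits baseline lesion counts that plausibly predict later IGA, so some precision is probably lost

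*SAP*

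**What the plan says.** SAP 7.5.2.7 fits facial IGA change with treatment, visit, treatment by visit and "baseline facial IGA score as the only continuous variable". No lesion count appears.

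Protocol 5.1, criterion 2, admits subjects with a facial IGA of 3 or 4 only. The same criterion requires "At least 20 and no more than 100 inflammatory lesions on the face" and caps noninflammatory lesions at 100. The Schedule of Activities (Protocol 1.3) takes IGA and counts together at screening, Day 1 and every later visit, with the order fixed: "Facial IGA must be performed before facial lesion count".

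The primary lesion-count MMRM (SAP 7.5.1) carries two severity covariates: "facial IGA score at baseline (Grade 3 vs. 4) as categorical covariates and the baseline value of response as the only continuous covariate".

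The other facial IGA analyses also use baseline IGA alone, or nothing:
- The exploratory Week 12 analysis is done "using an ordinal logistic regression model with treatment, facial IGA score at baseline (Grade 3 vs. 4) as categorical covariates" (SAP 7.5.2.7).
- The responder difference is "estimated by an unadjusted risk difference in proportions with 90% exact unconditional CIs", with a CMH test stratified by baseline IGA (SAP 7.5.2.8).
- For the exploratory responder GEE: "The model will include treatment, visit, treatment by visit interaction, and baseline facial IGA score as categorical covariates" (SAP 7.5.2.8).

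The sensitivity models that add sex, site or smoking apply to the primary endpoint only (SAP 7.5.4). Secondary testing is exploratory at two-sided 0.10 (Protocol 9.1, SAP 3.3), without multiplicity adjustment (SAP 7.5).

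**The concern.** A covariate that takes two values can explain only the difference between two groups of subjects. Protocol Appendix 8 defines the grades by how much of the face is involved and by the amount of comedones, papules and pustules. Baseline counts are therefore a finer measure of one of the two things the scale grades. If they predict Week 12 IGA among subjects with the same baseline grade, leaving them out puts explainable variation into the residual.

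Randomization is stratified on IGA but not on counts. With about 36 evaluable subjects per arm, counts may differ between arms by chance, and the planned model does not absorb that difference. At stake is the width of the confidence intervals for the IGA change, not the validity of the comparison.

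**Working it through.** **1. The plan's own power figure.** This exists only for the primary endpoint: difference 6.1, SD 10.4, 36 per arm, two-sided 0.10 (Protocol 9.2, SAP 3.5).
- 6.1 / (10.4 × √(2/36)) = 6.1 / 2.451 = 2.489
- 2.489 − 1.645 = 0.844, giving power of 80.1% by the normal approximation; the t-test gives 79.4%.

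The stated 80% reproduces. The documents give no SD, effect size or power for any facial IGA endpoint.

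**2. Effect of adding baseline counts at Week 12.** Inputs: N = 108 evaluable (SAP 3.5). R² is the partial R² of the added counts for Week 12 IGA change, given treatment and baseline IGA. The documents do not give it, so it is assumed over a range.

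For one added count, the variance of the treatment contrast is multiplied by (1 − R²) × (1 + 1/(N − 6)) = (1 − R²) × 103/102. A second count multiplies by a further 102/101, so for two counts the factor is (1 − R²) × 103/101. The SE ratio is the square root, and the equivalent sample size is 36 divided by the factor.

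| Partial R² (assumed) | SE, one count | Equivalent n per arm | SE, two counts | Equivalent n per arm |
|---|---|---|---|---|
| 0 | +0.5% | 35.7 | +1.0% | 35.3 |
| 0.05 | −2.1% | 37.5 | −1.6% | 37.2 |
| 0.10 | −4.7% | 39.6 | −4.2% | 39.2 |
| 0.20 | −10.1% | 44.6 | −9.7% | 44.1 |

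Example, two counts at 0.10: 0.90 × 1.0198 = 0.918; √0.918 = 0.958; 36/0.918 = 39.2. In the two-count columns, R² is the joint value for both counts.

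Break-even is R² = 1/103 = 0.0097 for one count and 2/103 = 0.019 for two.

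**3. On the power scale (one count).** For a hypothetical IGA effect with 80% power under the planned model, power becomes 79.7%, 81.4%, 83.2% and 86.9% at R² of 0, 0.05, 0.10 and 0.20.

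**4. Check by simulation.** Five-level IGA data were simulated with 36 per arm, one count added, 4,000 trials per setting and parameters chosen only for illustration. Power was unchanged with no association (68.3% and 68.1%). At partial R² of about 0.03, 0.08 and 0.14 it went from 68.3% to 68.4%, 66.4% to 69.2% and 62.4% to 67.5%. The gain is modest and negligible when the association is weak.

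**5. Limit of the formula.** It describes a linear model at one visit, as an approximation to the MMRM. It does not carry over to the odds ratios of the ordinal model or the GEE.

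**The case against.** The strongest answer is that the SAP follows a consistent rule: each model adjusts for the baseline of its own response and for the stratification factor. For facial IGA these are the same variable, so one term remains. A reader comparing SAP 7.5.1 with 7.5.2.7 might infer that the count was dropped by mistake. The documents do not support that: the count is in the primary model because it is that model's own baseline. This part of the objection stands, and the point is an improvement, not the correction of an error.

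Three other inferences also go too far:
- *That facial IGA is the main secondary endpoint.* The secondary endpoints are an unranked list, all tested as exploratory.
- *That subjects within one grade span 20 to 100 inflammatory lesions.* Those limits apply to the whole trial, and the grade descriptions suggest narrower ranges within each grade. The scale also grades surface area, which counts do not measure. The association may therefore be weaker than it first appears.
- *That chance imbalance in counts makes the planned comparison misleading.* Randomization keeps it valid and its standard error already allows for such imbalance. SAP 6.1.1 summarizes baseline counts by arm, so any imbalance will be visible.

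What the objection does not remove is that a plausible predictor, already collected, goes unused where the only severity covariate has two levels.

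**Conclusion.** The point holds as a low-cost gain in precision for the facial IGA MMRM. The expected size is a standard error about 2% to 10% smaller if the partial R² is 0.05 to 0.20, against about 0.5% larger per count if it is zero. This rests on an assumed association that the Appendix 8 wording makes plausible but that no figure in the documents establishes. A loss of precision is therefore probable, not demonstrated, and the power figures start from a hypothetical 80%.

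A reader might also infer that the responder endpoint would gain in the same way. It would not under the planned analysis: the risk difference is unadjusted and the CMH test is stratified by IGA only, so neither is affected. In the ordinal model and the GEE, adding a prognostic covariate changes the conditional odds ratio being estimated.

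**What to change.** Before the Week 12 primary analysis is unblinded, amend SAP 7.5.2.7 so that the facial IGA MMRM includes baseline facial inflammatory and noninflammatory lesion counts as continuous covariates, keeping baseline facial IGA. Update the model template in SAP Appendix 2 to match. Because SAP 7.1 applies this MMRM to the multiply imputed IGA data, put the two counts in that imputation model as well.

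For the exploratory ordinal model and responder GEE the addition is optional. If it is made, state that the odds ratio is then conditional on the counts. If a precision gain is wanted for the responder difference, specify a standardised risk difference alongside the unadjusted one. The GEE already has a fallback for convergence trouble, which is a reason for restraint there.

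The cost is a few lines of SAP text and code and two degrees of freedom. Eligibility requires both counts on Day 1, so no new data are needed and no eligible randomized subject should lack them.
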